9.2 Protocol Deviations

A prospectively defined protocol deviation plan will be followed to identify instances of major deviations from the study protocol. In general, major protocol deviations are defined as those having a direct negative effect on the rights, safety, well-being of study subjects, or the integrity of the data for key conclusions related to efficacy or safety. Major protocol deviations will be grouped by type of deviations in the summary table. Within each type, number (%) of subjects with a specific deviation will be presented. In addition, listing(s) of individual subjects with major deviations will be generated.

9.3 Demographic and Baseline Characteristics

9.3.1 Demographic Characteristics

The following summaries will be provided by treatment group and based on the ITT Analysis Set:

- Demographic characteristics including age, sex, race, and ethnicity. Subjects may be included in more than one racial category if so reported in the eCRF. In addition to summarization as a continuous variable, age will also be categorized and frequencies will be presented for age categories ≥ 18 -<65, ≥ 65 -<74, ≥ 75 -<85, and ≥ 85
- Distribution of subjects across region and country
- Demographic characteristics by region

9.3.2 Baseline characteristics

Baseline characteristics will be summarized as follows overall and by region based on the ITT Analysis Set:

- Height (cm), weight (kg), BMI (kg/m^2) will be summarized as appropriate to continuous variables
- Renal function based on eGFR values categorized as normal (eGFR $\geq 90 \text{ mL}/\text{min}/1.73 \text{ m}^2$), mild impairment (eGFR ≥ 60 -<90 $\text{mL}/\text{min}/1.73 \text{ m}^2$), moderate impairment (eGFR ≥ 30 -<60 $\text{mL}/\text{min}/1.73 \text{ m}^2$), and severe impairment (eGFR <30 $\text{mL}/\text{min}/1.73 \text{ m}^2$)
- Baseline HDL ($\mu\text{mol}/\text{L}$), LDL ($\mu\text{mol}/\text{L}$), cholesterol ($\mu\text{mol}/\text{L}$), and triglycerides ($\mu\text{mol}/\text{L}$) will be summarized as continuous variables
- Baseline HDL categorized as normal or low using gender-specific cut points
 - Male: < 1.04 $\mu\text{mol}/\text{L}$ (<40 mg/dL)
 - Female: <1.3 $\mu\text{mol}/\text{L}$ (<50 mg/dL)

- Characteristics of Index MI at presenting hospital:
 - Number of angina events in the 24 hours prior to presentation
 - ECG with significant ST segment deviation (yes, no)
 - Killip Class (I, II)
 - Heart rate and blood pressure
- Characteristics of Index MI
 - Type (STEMI or NSTEMI)
 - Management type – PCI or medically managed
 - Whether or not coronary angiography is performed and if yes, present:
 - Receipt of prophylaxis for contrast-induced nephropathy
 - Prophylaxis type
 - Multivessel disease (MVD) assessment
 - Location of stenosis $\geq 50\%$
 - Identification of infarct-related artery
 - Medications of interest taken prior to the index MI and used to treat index MI
 - If percutaneous coronary revascularization is performed, type and location of treated vessel(s) will be presented
 - Left ventricular ejection fraction (LVEF) in those assessed

9.3.3 Targeted and Other Medical History

The following targeted medical history at screening will be summarized by treatment group and by region based on the ITT Analysis Set to describe the patient population enrolled in the study:

- Known coronary artery disease
- Prior MI excluding index MI
- Prior (excluding index MI) coronary revascularization performed and if yes, type of procedure
- Chronic kidney disease
- History of congestive heart failure within the past year
- Peripheral Artery Disease

- Moderate to severe valvular heart disease
- Atrial fibrillation
- Cerebrovascular disease and if yes:
 - Transient ischemic attack (TIA)
 - Ischemic stroke
 - Hemorrhagic stroke
 - Carotid endarterectomy
 - Carotid stenting
- Hypertension
- Gilbert's syndrome
- Hypercholesterolemia or use of medication for hypercholesterolemia prior to index MI
- Diabetes mellitus – type and pharmacotherapy for diabetes will be summarized. In addition, diabetes mellitus on pharmacotherapy is defined as receipt of oral medication, insulin or other non-insulin injectable while diet therapy only or no treatment are considered as not meeting the criterion.
- Smoking or tobacco usage – current or former user
- e-cigarette usage – current or former

By subject listing of all medical history will be produced.

9.4 Prior and Concomitant Medications

The ITT Analysis Set will be used for describing medication usage during the study. Prior ACS-related medications taken by subjects in the 4 weeks before screening will be collected in a targeted manner. The number (%) of subjects receiving each medication of interest will be summarized.

Medication usage from the time of informed consent through 90 days from randomization will be captured. Medications intended to diagnose or treat SAEs will be captured through the end of study. All medications will be coded using the WHO Drug coding dictionary and summarized to show the number and percentage of subjects taking concomitant medications. Anatomical Therapeutic Chemical (ATC) classification Level 1 (Body System) information will be included in the dataset created but will not appear on the listing or summary.

Medications will be grouped by ATC code and summarized in alphabetical order by generic

term within ATC code. Subjects with multiple instances of the same medication will be counted once in the summary table(s).

The following output will be generated:

- Summary of Concomitant Medications through 90 days
- Summary of Concomitant Medications through End of Study
- ACS-related concomitant Medications of Interest including:
 - Aspirin
 - P2Y12 anti-platelets
 - PCSK9 inhibitors (PCSK9i)
 - Beta-blockers
 - ACE-I or ARB
 - Statins will be categorized as high, moderate, or low intensity, and none
 - Non-statin lipid-modifying agents

The number (%) of subjects receiving aspirin, statins, and P2Y12 inhibitors will be presented at study days 90, 180, and 365 for ascertaining the degree of compliance with evidence-based therapy; reasons for not doing so will be summarized with number (%) of subjects presented for each medication and reason.

Identification of ACS-related Medications:

Concomitant medications will be categorized as belonging to one or more of predefined ACS-related drug classes of interest as follows: a comprehensive list of individual medications within each drug class of interest will be prospectively generated from the WHO drug dictionary, retaining the associated ATC level 4 code and preferred code for each medication. For statins, the list is also populated with dosages corresponding to low, moderate, or high intensity as defined by practice guidelines. This list will be merged with the coded concomitant medications usage data in the study database by ATC level 4 and preferred terms to identify matching records. The database will contain one record per subject and medication received when there is a match.

9.5 Prior and Concomitant Procedures

The number (%) of subjects undergoing a PCI for the index MI will be summarized based on the ITT Analysis Set. Additional coronary revascularizations planned at the time of index MI (ie, staged PCIs) will be summarized as occurring before or after randomization. Planned procedures which are performed after randomization and adjudicated by the CEC will be identified based on the procedure type and adjudication outcome (procedure type = PCI, procedure date is after randomization date, adjudication criteria are not met, or criteria are met and adjudicated as an elective, staged procedure). All coronary revascularization procedures occurring post-randomization will be adjudicated by the CEC. The number (%) of subjects undergoing coronary revascularization will be summarized as adjudicated through 90 days, and 365 days. This table will include the total number of procedures undergone by study subjects. In each period, the type of procedure as well as elective (staged, non-staged, or unplanned) or urgent nature of the procedure will be summarized. Procedures not reported by investigator but identified during back end review of study data and triggered for adjudication will be included.

All investigator-reported procedures for cerebral or peripheral ischemia reported on or after randomization through study Day 90, Day 91-180, and Day 181-365 will be summarized using the ITT Analysis Set and will present the number (%) of subjects undergoing a procedure by type and treatment group.

Supporting listing of individual subject data will be generated for prior and concomitant procedures.

The exploratory endpoint, select surgeries and procedures related to hospitalization for coronary, cerebral, or peripheral ischemia will consider all revascularization procedures occurring during a positively-adjudicated hospitalization for ischemia. This analysis will count procedures with dates contained within admission and discharge dates as reported by investigator or within 10 days following admission date if the discharge date is not available. Positive adjudication of triggered coronary revascularization procedures will also be included based on the CEC-reported procedure date.

Site-reported hospitalizations will be used in summarizing and analyzing endpoints related to medical resource utilization with the exception of select surgeries and procedures which is described above. Post-hospitalization discharge status will be presented for site-reported and positively adjudicated ischemic hospitalization events. Hospitalizations may be new or prolongation of an existing one. The index MI hospitalization extending past the date of

randomization will be excluded unless the extension is due to a treatment-emergent serious adverse event. Overlapping hospitalization dates will count as a single event with the longest duration utilized in analysis. A supporting listing of individual subject data will be provided.

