#### **10.3.2.4.1      Exploratory Efficacy Analyses**

The analyses of the exploratory efficacy endpoints will be based on the ITT Analysis Set.

The total number of hospitalizations from the time of randomization through 30 days will be analyzed using a negative binomial regression model in a similar manner as described in [Section 10.3.2.3.1.1](#) for the number of hospitalizations through 90 days.

The exploratory time to event efficacy endpoints listed in 2 to 6 above, will be analyzed in a manner similar to that of the primary endpoint (see [Section 10.3.2.2.1](#)). Treatment comparison will be based on a covariate-adjusted Cox regression model for estimating the 1-sided Wald  $P$  value, the hazard ratio and its 2-sided 95% confidence interval. The effect over time will be illustrated with a plot of the complement  $(1 - KM)$  KM estimates. Event counts and percentages will be presented.

The analysis of the endpoint, total occurrence of rehospitalizations for CV events and all-cause death from the time of randomization through 90 days, will be based on the unmatched Win Ratio [[Pocock et al, 2012](#)], as described in [Section 10.3.2.3.1](#).

The exploratory endpoints including total occurrence of CV death, MI, and stroke from the time of randomization through 90, 180, and 365 days and total occurrence of all-cause death, MI, and stroke from the time of randomization through 90, 180, and 365 days will be analyzed using a negative binomial regression model in a similar manner as described in [Section 10.3.2.3.1.1](#) for the number of hospitalizations through 90 days.

The relationship between medical resource utilization and treatment with CSL112 will be explored and characterized using descriptive statistics. For the purpose of data analysis, the medical resource utilization endpoints including number of hospitalizations, length of stay and days in ICU or CCU will be treated as count data. For each subject, the following results will be derived across all hospitalizations occurring during the 90 days from randomization: total number of hospitalizations, total number of days hospitalized and the total number of

days spent in ICU or CCU. The analysis of these endpoints will be performed using a negative binomial regression model in a similar approach to that described for CV hospitalizations. Treatment comparisons will be based on the resulting incidence ratio, 95% confidence interval, and 1-sided  $P$  value obtained from the model.

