8.2.4 Durations

Durations of events (eg, duration of an AE or medication) calculated in days will use only dates based on the algorithm given below:

- (End date – Start date) + 1

Durations calculated in hours (h), such as duration of infusion, will be calculated using date/time variables shown below:

- (End date/time – Start date/time)

Where durations calculated in days have to be reported in months or years, the following approach will be taken:

$$\text{Months} = \text{days} / 30.4375$$

$$\text{Years} = \text{days} / 365.25$$

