8.2.9 Derivation Algorithms

Derivation of BMI

BMI will be calculated using the following formula:

$$\text{BMI (kg/m}^2\text{)} = \text{Weight (kg)} / [\text{Height (m)}]^2$$

The height and weight measured at Screening will be used (if available).

Derivation of Hospitalizations for coronary, cerebral, or peripheral ischemia:

- Total number of hospitalizations per subject will be derived by defining a cumulative count variable that is incremented with each new date of positively-adjudicated hospitalization. The analysis dataset will include one record per subject, with a count variable containing the total number of hospitalizations.

Derivation of Indirect bilirubin:

The calculation of indirect bilirubin is applicable when both TBili and direct bilirubin are reported by the central laboratory.

- Indirect bilirubin ($\mu\text{mol/L}$) = TBili ($\mu\text{mol/L}$) – direct bilirubin ($\mu\text{mol/L}$)

Derivation of Estimated Glomerular Filtration Rate (eGFR):

For the purpose of safety analyses, the eGFR value will be calculated for both local and central laboratory reported results. The CKD-EPI equations shown in [Table 8-1](#) will be used:

Table 8-1 **CKD-EPI Equations**

Race and Sex	Serum Creatinine (mg/dL (μ mol/L))	Equation
Black		
Female	≤ 0.7 (≤ 62)	$eGFR = 166 * (Scr/0.7)^{-0.329} * 0.993^{age}$
	> 0.7 (> 62)	$eGFR = 166 * (Scr/0.7)^{-1.209} * 0.993^{age}$
Male	≤ 0.9 (≤ 80)	$eGFR = 163 * (Scr/0.9)^{-0.411} * 0.993^{age}$
	> 0.9 (> 80)	$eGFR = 163 * (Scr/0.9)^{-1.209} * 0.993^{age}$
White or Other		
Female	≤ 0.7 (≤ 62)	$eGFR = 144 * (Scr/0.7)^{-0.329} * 0.993^{age}$
	> 0.7 (> 62)	$eGFR = 144 * (Scr/0.7)^{-1.209} * 0.993^{age}$
Male	≤ 0.9 (≤ 80)	$eGFR = 141 * (Scr/0.9)^{-0.411} * 0.993^{age}$
	> 0.9 (> 80)	$eGFR = 141 * (Scr/0.9)^{-1.209} * 0.993^{age}$

The CKD-EPI equation can be expressed in a single equation as:

- $eGFR \text{ (derived)} = 141 * \min(Scr/\kappa, 1)^\alpha * \max(Scr/\kappa, 1)^{-1.209} * 0.993^{age} * 1.018 \text{ [if female]}$
 $\text{ x } 1.159 \text{ [if black]}$

Where Scr is serum creatinine, κ is 0.7 for females and 0.9 for males, α is -0.329 for females and -0.411 for males, min indicates the minimum of Scr/κ or 1, and max indicates the maximum of Scr/κ or 1. In Table 8-1, the multiplication factors for race and sex are incorporated into the intercept, which results in the different intercepts for race and sex combinations.

Stratification and Prognostic Factors

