10.2 Analysis of Key Secondary Endpoints

The key secondary endpoints will be analyzed based on the ITT population. The null hypothesis associated with each key secondary endpoint will be tested at the time of final analysis. The analysis will be based on CEC-adjudicated events and an assessment of concordance between the investigator-reported and CEC adjudicated events will be undertaken. Multiplicity adjustments are discussed in [Section 7.4](#).

The three key secondary endpoints and their planned analyses are given below:

10.2.1 Total number of hospitalizations for coronary, cerebral, or peripheral ischemia through 90 days after randomization

A negative binomial regression model will be fitted to the count data arising from the number of hospitalizations. This analysis will consider only those hospitalizations adjudicated by the CEC as meeting endpoint criteria. The model will include fixed effects for treatment, region, index MI type, and index MI management, age (as a continuous variable), diabetes, peripheral artery disease, and history of MI, and a term for interaction between index MI type and index MI management which correspond to the covariates in the primary analysis. The log link function will be used and the log-transformed duration of follow-up (based on the date of last MACE ascertainment) within 90 days will be included in the model to account for the variable duration of follow-up across subjects. However, if the model fails to converge then the offset statement will be excluded. The mean rate of hospitalization per 90 days will

be presented by treatment arm. A 1-sided P value for treatment comparison, the rate ratio (CSL112: placebo) and its 95% CI will be estimated from the model.

A cumulative plot of recurrent hospitalization events will be generated using a non-parametric estimator for the mean cumulative function (MCF). Nelson [[Nelson, 2003](#)] introduced the MCF as a way to summarize the average number of events occurring in a subject by time t , within a population exposed to censoring events such as losses to follow-up and termination of the study. It assumes non-informative censoring and the risk set decreases only when an individual is removed from follow-up. A supportive data listing of hospitalization data will be produced.

The SAS code for fitting a negative binomial regression model to the count data from hospitalizations is given in [Appendix 15.5](#).

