The relationship between medical resource utilization and treatment with CSL112 will be descriptively summarized. The endpoints of medical resource utilization including the number of hospitalizations, length of hospital stay (days), CCU or ICU stay (days) and number of select surgeries/select procedures related to hospitalization for coronary, cerebral, or peripheral ischemia will be treated as count data for the purpose of analysis. For each subject, total counts either in number of admissions or duration of stay will be derived across all hospitalizations occurring during the 90 day period from randomization. The analyses of these endpoints will use a negative binomial regression model as described for the key secondary endpoint of CV hospitalizations described in [Section 10.2.1](#). Discharge to following CV hospitalization will be descriptively summarized with counts and percentages in each category by treatment arm.

The EQ-5D-3L is a patient self-assessment of five dimensions of health-related quality of life: mobility, self-care, usual activities, pain or discomfort and anxiety or depression. Each dimension is measured on a 3-point scale where a higher score corresponds to a worse health state. Scores from the individual dimensions will be used to calculate an overall utility score for each patient using the algorithm specified by the developers of the instrument [[EuroQoL, 2015](#)]. The EQ VAS is a continuous 100 point integer scale from 0 (the worst health you can imagine) to 100 (the best health you can imagine). Further details can be found in [Appendix 15.2](#).

Response to each of the five dimensions will be descriptively summarized. For each dimension and treatment, shift tables will be employed indicating the number of subjects whose response falls into a grid defined by the baseline value on one axis and the post-treatment value on the other axis. To compare treatments on each dimension, the number (%) of subjects with improvement, no change, or worsening from baseline to the post-treatment value will be analyzed using a chi-square test for a 2 x 3 contingency table with ordered categories of response.

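### SAP 9.5 keeps the longest duration when hospital stays overlap; read literally, this understates days in hospital for staggered stays

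*SAP*

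**What the plan says.** The rule stands in a paragraph of SAP 9.5 whose scope is resource use: "Site-reported hospitalizations will be used in summarizing and analyzing endpoints related to medical resource utilization", with an exception for select surgeries and procedures. For overlaps it says: "Overlapping hospitalization dates will count as a single event with the longest duration utilized in analysis".

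The quantity to be measured is defined elsewhere. Protocol 10.3.2.4.1 derives, for each subject, the "total number of hospitalizations, total number of days hospitalized" and the days spent in ICU or CCU. SAP 10.4 says that "total counts either in number of admissions or duration of stay will be derived across all hospitalizations occurring during the 90 day period". SAP 8.2.4 computes durations in days as end date minus start date plus 1.

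The key secondary count of ischemic hospitalizations is derived separately. SAP 8.2.9 defines it as "a cumulative count variable that is incremented with each new date of positively-adjudicated hospitalization", and SAP 10.2.1 adds: "This analysis will consider only those hospitalizations adjudicated by the CEC as meeting endpoint criteria". Neither section has an overlap rule.

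**The concern.** Once overlapping records have become one event, the days in hospital run from the earliest admission to the latest discharge. Taking the longest single record gives that number only if one record contains the others. When a subject is admitted elsewhere before or on the day that the first stay ends, each record covers part of the time and the longest one leaves some of it out.

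At stake is the accuracy of length of stay through 90 days, and through 180 and 365 days in the additional exploratory list of SAP 10.4. ICU/CCU days share the problem: both documents total them across hospitalizations, but nothing says what becomes of ICU/CCU days on a record whose duration is not used.

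**Working it through.** The plan states no figure that depends on this rule, so there is none to reproduce. The check applies the SAP 8.2.4 formula to example stays. The days are illustrative; the formula and the rule are the SAP's.

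Main example:
- Days 10-13: 13 − 10 + 1 = 4 days.
- Days 13-20: 20 − 13 + 1 = 8 days.
- Merged span, Days 10-20: 20 − 10 + 1 = 11 days.
- Literal rule: max(4, 8) = 8 days. Shortfall: 11 − 8 = 3 days, and 3/11 = 27%.

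In general, if the longer stay lasts *a* days, the shorter *b* days, and they share *k* days, the span is *a + b − k*. The longest record gives *a*, so the shortfall is *b − k*. Here that is 4 − 1 = 3. It is zero when the shorter stay lies wholly inside the longer one (*b = k*), which includes a one-day stay on the shared date.

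| Stays (days) | Record lengths | Value under the literal rule | Days in hospital | Short by |
|---|---|---|---|---|
| 10-12, 12-19 | 3, 8 | 8 | 10 | 2 (20%) |
| 10-14, 14-18 | 5, 5 | 5 | 9 | 4 (44%) |
| 10-12, 12-16, 16-19 | 3, 5, 4 | 5 | 10 | 5 (50%) |
| 10-19, 12-15 (nested) | 10, 4 | 10 | 10 | 0 |
| 10-10, 10-17 (one-day first stay) | 1, 8 | 8 | 8 | 0 |
| 10-12, 13-19 (no shared date) | 3, 7 | not triggered; 3 + 7 = 10 | 10 | 0 |

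Trial-wide size needs a frequency that the documents do not give. Assume that a share *s* of all hospital days falls in staggered overlaps and that a fraction *f* of those days is lost. Total days are then understated by *s × f*:
- *f* = 3/11: *s* = 2% gives 0.02 × 0.273 = 0.5%; *s* = 20% gives 0.20 × 0.273 = 5.5%.
- *f* = 50%: *s* = 2% gives 1%; *s* = 20% gives 10%.

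If *s × f* is the same in both arms, the factor (1 − *s × f*) cancels from a simple ratio of mean days. The reported days are then too low, but the treatment comparison does not move.

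**The case against.** The best reply is that the sentence can be read the other way. Overlapping dates become a single event, and the longest duration of that event could be its full span. The stated target, total days hospitalized, favours that reading. This is possible, but the sentence does not say it. Its more natural sense is a choice among the durations on record, and two programmers could derive different values from it. Making the span explicit costs nothing if it was what was meant.

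It is also fair that the affected set is narrow: the stays must share a date and neither may contain the other. Stays on consecutive days do not trigger the rule and are summed, so nothing is lost there. The endpoints are exploratory, and SAP 10.4 calls their P values descriptive. All of this stands and limits the point.

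A reader might go further and infer that the formally tested hospitalization count (H02 in SAP 7.4) counts one continuous stay twice, because 8.2.9 adds one per new date and has no merge rule. The documents do not support that as an error:
- Only hospitalizations confirmed by the CEC enter the count. Its definitions are in a separate charter that was not available, and the protocol and SAP neither show nor exclude that both parts of one stay would be confirmed.
- Neither document mentions inter-hospital transfer or gives a rate for it.
- A second positively adjudicated date within one stay may be a genuine new event.
- The two counts differ in purpose and source (all site-reported stays against confirmed ischemic ones), so different rules are not in themselves a contradiction.

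**Conclusion.** The point holds for SAP 9.5 on its literal reading. Length of stay is understated for staggered overlaps in which each stay extends beyond the shared days: by 3 of 11 days in the main example, and by 20% to 50% in the others. Nested and non-overlapping stays are unaffected. Only the exploratory resource-use endpoints are touched. The trial-wide effect depends on an unknown frequency of overlap, and it need not bias the comparison if overlaps are similar by arm. Nothing in the documents shows that the affected subjects are sicker than others.

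For the key secondary count, what remains is a request for clarification. For scale only, assume Poisson episodes and that a share *t* of them is counted twice in both arms. The mean count is multiplied by 1 + *t* and the variance of the log rate ratio by (1 + 3*t*)/(1 + *t*)². For *t* = 2% that is 1.06/1.0404 = 1.019; for *t* = 20% it is 1.60/1.44 = 1.111. The rate ratio itself does not change. Even then the cost would be some precision rather than a shift in the estimate.

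**What to change.** - **SAP 9.5:** state that site-reported stays with overlapping dates are merged into one event, with duration = latest discharge − earliest admission + 1, and that ICU/CCU days are counted as the union of calendar days across the merged records.
- **SAP 8.2.9:** name the date that increments the count (for example admission or adjudicated event date), and cite or confirm the CEC charter's rule on when two records belong to the same episode. Do not impose one count per merged stay. That would change a formally tested endpoint and could erase a genuine second adjudicated event.

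The cost is a few lines of SAP text and a standard interval-merge step in the derivation of the resource-use data. The number of merged events does not change, because overlapping dates already count once. No sample size, power or alpha figure changes.
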